4.2.2 Secondary endpoints

4.2.2.1 Supportive secondary endpoints

Supportive secondary efficacy endpoints:

- Daily insulin dose after 26 weeks
- Change from baseline in body weight after 26 weeks*
- Responder after 26 weeks (yes/no):
 - HbA_{1c} < 7.0%
 - HbA_{1c} < 7.0% and without weight gain
 - HbA_{1c} < 7.0% without treatment emergent severe or BG confirmed symptomatic hypoglycaemic episodes during the last 12 weeks of treatment
 - HbA_{1c} < 7.0% and without weight gain and without treatment emergent severe or BG confirmed symptomatic hypoglycaemic episodes during the last 12 weeks of treatment
 - HbA_{1c} ≤ 6.5%
 - HbA_{1c} ≤ 6.5% and without weight gain
 - HbA_{1c} ≤ 6.5% without treatment emergent severe or BG confirmed symptomatic hypoglycaemic episodes during the last 12 weeks of treatment
 - HbA_{1c} ≤ 6.5% and without weight gain and without treatment emergent severe or BG confirmed symptomatic hypoglycaemic episodes during the last 12 weeks of treatment

- Change from baseline after 26 weeks in:
 - FPG*
 - Waist circumference
 - Blood pressure (systolic and diastolic)
 - Self-measured blood glucose (SMBG) 9-point profile
 - 9-point profile (individual points in the profile)
 - Mean of the 9-point profile
 - Mean of postprandial plasma glucose increments (from before meal to 90 min after breakfast, lunch and dinner). The mean increment over all meals will be derived as the mean of all available meal increments
- Lipid profile after 26 weeks of treatment

Supportive secondary safety endpoints:

- Number of treatment emergent adverse events (TEAE) during 26 weeks of treatment
- Number of treatment emergent severe or BG confirmed hypoglycaemic episodes during 26 weeks of treatment*
- Number of treatment emergent severe or BG confirmed symptomatic hypoglycaemic episodes during 26 weeks of treatment
- Number of treatment emergent hypoglycaemic episodes according to ADA definition during 26 weeks of treatment
- Number of treatment emergent nocturnal severe or BG confirmed symptomatic hypoglycaemic episodes during 26 weeks of treatment
- Change from baseline in clinical evaluation after 26 weeks of treatment:
 - Physical examination
 - Fundoscopy or fundus photography
 - Electrocardiogram (ECG)
 - Pulse
- Change from baseline in laboratory assessments after 26 weeks of treatment:
 - Biochemistry (including amylase and lipase)
 - Haematology
 - Calcitonin

Supportive secondary patient reported outcome endpoints:

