8.7.4 Diaries

At each site visit the subjects will be provided with a new diary. The diary must be collected at the next site visit, and retained at the site as source data. However, after ET (V32), the diary data at the FU contact (P33) will be collected per phone. Consequently, source data from the FU contact (P33) will be the notes written by the investigator in the subject's medical record and based on an interview.

The investigator is only allowed to record the following data in the diary:

- Subject number
- Site contact details
- Time and date of next visit or phone contact
- Prescribed dose of trial product
- Prescribed metformin treatment
- Prescribed diabetes treatment at V32
- Doses and values from SMBG measurements from previous diary, if required to complete next dose adjustment
- Review signature and date

The subject must record the following information in the diary:

- Date and value of the daily pre-breakfast SMBG (see section [8.4.1](#))
- Date, actual clock time and value of the 9-point profile SMBG prior to V2, V18 and V32 (see section [8.4.1.1](#))

- Date and dose of trial product each day
 - Time for the first and the last trial product dose taken when randomised and at ET, respectively
- Hypoglycaemic episodes (see section [8.5.7](#))
- Medical issues
- Changes to concomitant medication (see section [8.3.4](#))
- Changes in total daily dose of metformin (see section [8.3.4.1](#))

If the subject is not able to complete the diary and need assistance from a third party to complete the diary, this must be stated in the subject's medical records.

Based on the values from the SMBG measurements, the investigator/subject will assess whether trial product dose needs adjustment according to the titration guideline ([Appendix A](#)).

The diary must be reviewed by the investigator to ensure that AEs, including medical issues and concomitant medication, are reported (see section [8.3.4](#), [8.5.1](#) and [12.2](#)). In addition, the investigator must ensure that the SMBG measurements are reported as hypoglycaemic episodes if required (see section [8.5.7](#)).

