Fasting plasma glucose (FPG)

Change from baseline in FPG after 26 weeks of treatment will be analysed using the standard ANCOVA model.

Waist circumference

Change from baseline in waist circumference after 26 weeks of treatment will be analysed using the standard ANCOVA model.

Blood pressure (systolic and diastolic)

Change from baseline in blood pressure after 26 weeks of treatment will be analysed using the standard ANCOVA model.

Self-measured blood glucose (SMBG) 9-point profile

The following six endpoints from the 9-point profile will be defined:

- 9-point profile (individual SMBG values) [One endpoint]
- Mean of the 9-point profile, defined as the area under the profile (calculated using the trapezoidal method) divided by the measurement time [One endpoint]
- Prandial plasma glucose increments (from before meal to 90 min after for breakfast, lunch and dinner). The mean increment over all meals will be derived as the mean of all available meal increments [Four endpoints]

A linear mixed effect model will be fitted to the 9-point SMBG profile data. The model will include treatment, pre-trial anti-diabetic treatment, time, the interaction between treatment and time and the interaction between pre-trial anti-diabetic treatment and time as fixed factors and subject as random effect. From the model mean profile by treatment and relevant treatment differences will be estimated and explored.

Change from baseline after 26 weeks of treatment in mean of the 9-point profile and post-prandial increment endpoints will be analysed separately using the standard ANCOVA model.

Lipids

Total cholesterol, low density lipoprotein cholesterol (LDL cholesterol), high density lipoprotein cholesterol (HDL cholesterol), very low density lipoprotein cholesterol (VLDL cholesterol), triglycerides, and free fatty acids after 26 weeks of treatment will be analysed separately by using the standard ANCOVA model. In these statistical analyses the endpoint will be log-transformed and so will the baseline covariate.

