Responder for HbA_{1c} without hypoglycaemic episodes and weight gain after 26 weeks of treatment will be defined as HbA_{1c} < 7.0% or ≤ 6.5% at ET, without treatment emergent severe or BG confirmed symptomatic hypoglycaemic episodes during the last 12 weeks of treatment, and change from baseline in body weight below or equal to zero. Analysis of each of the two responder endpoints will be based on a logistic regression model with treatment and pre-trial anti-diabetic treatment as fixed factors and baseline HbA_{1c} and body weight values as covariates.

Fasting plasma glucose (FPG)

Change from baseline in FPG after 26 weeks of treatment will be analysed using the standard ANCOVA model.

Waist circumference

Change from baseline in waist circumference after 26 weeks of treatment will be analysed using the standard ANCOVA model.

Blood pressure (systolic and diastolic)

Change from baseline in blood pressure after 26 weeks of treatment will be analysed using the standard ANCOVA model.

Self-measured blood glucose (SMBG) 9-point profile

The following six endpoints from the 9-point profile will be defined:

- 9-point profile (individual SMBG values) [One endpoint]
- Mean of the 9-point profile, defined as the area under the profile (calculated using the trapezoidal method) divided by the measurement time [One endpoint]
- Prandial plasma glucose increments (from before meal to 90 min after for breakfast, lunch and dinner). The mean increment over all meals will be derived as the mean of all available meal increments [Four endpoints]

A linear mixed effect model will be fitted to the 9-point SMBG profile data. The model will include treatment, pre-trial anti-diabetic treatment, time, the interaction between treatment and time and the interaction between pre-trial anti-diabetic treatment and time as fixed factors and subject as random effect. From the model mean profile by treatment and relevant treatment differences will be estimated and explored.

Change from baseline after 26 weeks of treatment in mean of the 9-point profile and post-prandial increment endpoints will be analysed separately using the standard ANCOVA model.

Lipids

Total cholesterol, low density lipoprotein cholesterol (LDL cholesterol), high density lipoprotein cholesterol (HDL cholesterol), very low density lipoprotein cholesterol (VLDL cholesterol),

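### The mixed model for the individual 9-point SMBG values omits the baseline glucose that is collected and used for the other five SMBG endpoints, which costs precision

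*SAP*

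**What the plan says.** Protocol 4.2.2.1 lists, under the item "Change from baseline after 26 weeks in", the sub-item "9-point profile (individual points in the profile". Protocol 8.7.4 has subjects record the "9-point profile SMBG prior to V2, V18 and V32", so a pre-randomisation profile exists.

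Protocol 17.4.1.1 states "A linear mixed effect model will be fitted to the 9-point SMBG profile data", and SAP 2.4.1.1 repeats it. The SAP's list of terms begins "The model will include treatment, pre-trial anti-diabetic treatment, time, the interaction between treatment and time" and ends with pre-trial treatment by time and a random subject effect. No glucose covariate appears. The output is described as "From the model mean profile by treatment and relevant treatment differences will be estimated and explored".

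The other five SMBG endpoints are the profile mean, "defined as the area under the profile (calculated using the trapezoidal method) divided by the measurement time", and four meal increments. For these the SAP says "Change from baseline after 26 weeks of treatment in mean of the 9-point profile and post-prandial increment endpoints will be analysed separately" with the standard ANCOVA. SAP section 2 defines that model as carrying the corresponding baseline value.

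The documents differ on the response for the sixth endpoint. The SAP's endpoint list labels it as individual SMBG values and mentions change from baseline only for the mean and increments. Protocol 4.2.2.1 places the individual points under change from baseline.

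**The concern.** Five of six endpoints from the same profile are adjusted for baseline and one is not, and no reason is given. The general ANCOVA statement in SAP section 2 does not supply the term, because this endpoint has its own explicit model. The random subject effect does not supply it either: if only V32 profiles are responses, that effect contains nothing from V2.

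What is at stake is the width of the confidence intervals for the point-by-point differences. There is also a smaller reporting issue. SAP section 2 asks for least-squares means of both the absolute value and the change, with a treatment difference, confidence interval and p-value. Without a baseline term, a model for the value and a model for the change will generally give different treatment differences, and the model sentence does not say which applies.

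**Working it through.** **The plan's figures.** The documents give no SD, correlation or power for SMBG, so there is no figure to reproduce for this endpoint. The one power figure concerns HbA1c (Protocol 17.1). The adjusted difference is 0.85 × 0.45 + 0.15 × 0.20 = 0.4125. With SD 1.0 and 105 per arm, a two-sided 5% t-test gives 84.5%, as stated. It does not bear on this point.

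**Inputs.** From the protocol: 105 per arm, nine points, baseline profile before V2. Assumed: equal variances at baseline and week 26, and r from 0.1 to 0.6.

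**Formulas.** For one point in the profile, the variance of the treatment difference is proportional to:

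- 1 for the week-26 value without baseline;
- 2(1 − r) for the change without baseline;
- 1 − r² for either response with baseline as covariate.

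So adjustment multiplies the variance of the value analysis by 1 − r², and the SE by its square root. An unadjusted change has 2(1 − r)/(1 − r²) = 2/(1 + r) times the adjusted variance.

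Pre-trial treatment is already in the model. If it explains 10% of the variance at both visits (assumption), the correlation left within strata is (r − 0.1)/0.9, that is 0, 0.111, 0.222 and 0.556.

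| r | 1 − r² | SE cut against value | SE cut, strata explain 10% | Change / adjusted variance |
|---|---|---|---|---|
| 0.1 | 0.99 | 0.5% | 0% | 1.82 |
| 0.2 | 0.96 | 2.0% | 0.6% | 1.67 |
| 0.3 | 0.91 | 4.6% | 2.5% | 1.54 |
| 0.6 | 0.64 | 20% | 16.9% | 1.25 |

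In sample-size terms, out of 105 per arm, the unadjusted value analysis is worth 105 × 0.99 = 104 at r = 0.1 and 105 × 0.64 = 67 at r = 0.6. The unadjusted change is worth 105/1.82 = 58 and 105/1.25 = 84.

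**Simulation check.** Complete data, nine-point random-intercept model, 105 per arm, four strata (assumed shares 30/30/20/20) with strata-by-time terms, within-profile correlation 0.4, true difference −0.40 SD, 500 runs. The adjusted/unadjusted variance ratios for the value at r = 0.1, 0.2, 0.3 and 0.6 were 1.007, 0.953, 0.899 and 0.656 with strata explaining nothing, and 1.005, 0.989, 0.953 and 0.694 with strata explaining 10%. Mean estimates were −0.395 to −0.401 with and without baseline, so no bias appeared. At r = 0.1 the extra slopes cost about as much as they gain.

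**Value or change.** With baseline and its interaction with time in the model, subtracting baseline from the response shifts only the baseline slopes. The two responses then gave treatment differences agreeing to within 1e-12.

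**The case against.** The strongest reply is that nothing important turns on this. The endpoint is supportive, is not among those marked for disclosure, has no decision rule, and its differences are only to be explored. An unadjusted randomised comparison is valid. The same nine points also feed the profile mean, which is baseline-adjusted. And r may well be low: each point is a single self-measured reading, pre-trial insulin and other OADs stop at randomisation, and both arms are titrated to a common fasting target. At low r, nine extra slopes and a missing-baseline rule buy almost nothing over the week-26 value.

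All of that stands as a case for low severity. It does not supply the missing term. The argument for low r is inference, since the documents give no correlation. If the change were the response, low r is where the loss is largest.

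Three stronger readings are tempting and not supported:

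- **Pooled visits.** No visit term is listed, so a reader might infer that the V2, V18 and V32 profiles are pooled and the week-26 difference diluted. Protocol 4.2.2.1 places the endpoint after 26 weeks, and time in a profile model reads naturally as the nine points. The unstated visit is a separate wording gap, not an effect of the missing covariate.
- **LOCF.** Carried-forward profiles can attenuate the difference, but they do so with or without a baseline term.
- **Change as the settled response.** The protocol's endpoint list points to change. The SAP's label of individual values, and its reserving of change for the mean and increments, favour the week-26 value. The change-score ratios therefore describe the less supported reading of the analysis text.

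**Conclusion.** The point holds as a matter of precision. The individual-point model leaves out a baseline that is collected and is used for the five sibling endpoints. A reader might infer a biased comparison, but under randomisation, with one week-26 response and complete data, the documents do not support that.

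The size is uncertain because r is assumed. The SE reduction against the week-26 value runs from negligible (0.5% at r = 0.1, or nil if strata explain 10% of the variance) to material (20%, or about 17%, at r = 0.6). Against an unadjusted change, the variance excess runs the other way, from 1.82 times at r = 0.1 to 1.25 times at r = 0.6, assuming equal variances. The severity is low, and neither the primary HbA1c conclusion nor its power is touched. It is worth making as a cheap improvement, together with reconciling the protocol's change wording with the SAP's value wording.

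**What to change.** In SAP 2.4.1.1, state that the response is the V32 profile value or its change from baseline. Add the subject's baseline SMBG at the same time point, and its interaction with time, as covariates. The choice of value or change then makes no difference to the treatment comparison, provided the change uses the same baseline value as the covariate.

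State a rule for missing baseline points, for example the baseline mean at that time point pooled over both arms. One is needed because the V2 profile is the first scheduled, so the general fallback to a screening value cannot apply. With a fraction m of baseline points filled this way, the variance ratio is about 1 − (1 − m)r². At r = 0.3 it is 0.92 (m = 10%) or 0.93 (m = 20%) instead of 0.91. At r = 0.6 it is 0.68 or 0.71 instead of 0.64.

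The cost is a few lines of SAP text and no new data. The downside is a few extra parameters, worth up to about 1% in variance if r is near 0.1.

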8.4 Efficacy assessments

8.4.1 Self-measured blood glucose (SMBG)

At screening (V1), subjects will be provided with a BG meter to be used for daily pre-breakfast SMBG measurements during the trial. The subjects will receive written instructions for use and demonstration on how to use the device including performance of regular calibrations according to the manufacturer's instructions. As necessary, the instructions will be repeated during the trial.

The BG meters use test strips calibrated to plasma values. Therefore, all measurements performed with capillary blood are automatically calibrated to plasma equivalent glucose values, which will be shown on the display.

Only the BG meter provided by Novo Nordisk should be used for the measurements required in the protocol.

Subjects should be instructed how to record the SMBGs in the diaries. The record of each pre-breakfast SMBG should include date and value. All data from the diary must be transcribed into the eCRF during or following the contact with site. If obtained via phone and a discrepancy is detected later on, the values in the eCRF should be corrected.

For SMBG values that meet the definition of a hypoglycaemic episode (see section [8.5.7](#)), relevant information must be registered in the subject diary and a hypoglycaemic episode form must be completed in the eCRF.

8.4.1.1 9-point self-measured blood glucose (SMBG) profile

Subjects will be instructed to perform a 9-point SMBG profile three times during the trial and record it in the diary. The 9-point SMBG profiles should include date and value in addition to actual clock time of each measurement. As for daily SMBGs, the data from the diary must be transcribed into the eCRF. The measurements should take place preferably within the week prior to the site visit on days where the subject does not anticipate unusual strenuous exercise.

The points of SMBG measurements starts with a pre-breakfast SMBG on day 1 and ends with a pre-breakfast SMBG on the following day as listed in [Table 8–1](#) below.

Table 8–1 9-point profile (SMBG)

Time point	Day 1	The following day
Pre-breakfast	√	√
90 min after start of breakfast	√	
Before lunch	√	
90 min after start of lunch	√	
Before dinner	√	
90 min after start of dinner	√	
At bedtime	√	
At 4 a.m.	√	

Trial product and metformin should be withheld until after the pre-breakfast SMBG measurements have been performed. Other prescribed concomitant medication can be taken as usual.

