Presentation of results from a statistical analysis will include the estimated mean treatment effects (Least Square Means [LSMeans]) for absolute values and change from baseline. In addition, estimated mean treatment difference (or ratio) will be presented together with the two-sided 95% confidence interval and corresponding two-sided p-value.

Handling of missing data

The expected percentage of missing data is around 15%. In accordance with industry guidance endpoints will be assessed at frequent visits. If an assessment was made both at screening (V1) and randomisation (V2), and if not otherwise specified, the value from the randomisation visit will be used as the baseline value. If the value measured at the randomisation visit is missing and the assessment also has been made at screening, then the screening value was used as the baseline value.

Missing values (including intermittent missing values) will be imputed using the LOCF method. Subjects without data after randomisation will be included by carrying forward their baseline value. LOCF has been a standard approach in diabetes trials for many years, and was used as the primary analysis in both IDegLira and IDeg phase 3 trials. LOCF is considered to be an appropriate method in the context of treat-to-target trials, where subjects after withdrawal typically continue their therapy using commercially available insulin. In previous treat-to-target trials with IDegLira and IDeg, LOCF has generally provided similar results to alternative methods applied to handle missing data, such as repeated measures models and completer analyses. In this trial, similar sensitivity analyses will be made to examine the robustness of the LOCF method

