2.3.1 Sensitivity analysis

Sensitivity analysis will be performed on FAS using the mixed model for repeated measurement (MMRM) to evaluate the robustness of using LOCF. All HbA_{1c} values available post baseline at scheduled measurement times will be analysed in a linear mixed normal model using an unstructured residual covariance matrix for HbA_{1c} measurements within the same subject. The model will include treatment, visit and pre-trial anti-diabetic treatment as fixed factors and baseline HbA_{1c} as covariate. Interactions between visit and all factors and between visit and baseline HbA_{1c} are also included in the model.

Further, a pattern mixture model approach, mimicking an intention-to-treat scenario will be applied. The imputation in the IDegLira arm will be based on IDeg values. It will be done as follows:

- In the first step intermittent missing values are imputed using a Markov Chain Monte Carlo method, in order to obtain a monotone missing data pattern. This imputation is done for each treatment group separately and 1000 copies of the dataset will be generated.
- In the second step, for each of the 1000 copies of the dataset, an analysis of variance model with treatment and pre-trial anti-diabetic treatment as fixed factors, and baseline HbA_{1c} as covariates is fitted to the change in HbA_{1c} from baseline to 4 weeks (V10) for the comparator group only. The estimated parameters, and their variances, from this model are used to impute missing values at 4 weeks for subjects in comparator and IDegLira treatment groups, based on pre-trial anti-diabetic treatment and HbA_{1c} at baseline.
- In the third step, for each of the 1000 copies of the dataset, missing HbA_{1c} values at 8 weeks (V14) are imputed in the same way as for 4 weeks. Now the imputations are based on an analysis of variance model with the same factors and the HbA_{1c} values at baseline and 4 weeks as covariates, fitted to the comparator group.
- This stepwise procedure is then repeated sequentially over the available planned visits, adding one visit in each step until the last planned visit at 26 weeks (V32)
- For each of the complete data sets, the change from baseline to 26 weeks is analysed using an analysis of variance model with treatment and pre-trial anti-diabetic treatment as fixed factors and baseline HbA_{1c} value as a covariate.

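### The nine-point SMBG model states no residual covariance; with the usual default all nine treatment differences share one standard error, so interval widths are wrong wherever variances differ by time point.

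*SAP*

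**What the plan says.** SAP 2.4.1.1 (Self-measured blood glucose 9-point profile) fits one linear mixed model to the profile data. The mean part has treatment, pre-trial anti-diabetic treatment, time, and the interactions of the first two with time. The random part is given only by the words "as fixed factors and subject as random effect". Protocol 17.4.1.1 specifies the same terms ("the interaction between treatment and time and the interaction between pre-trial anti-diabetic treatment and time as fixed factors and subject as random effect"), so the SAP adds no detail. Neither text mentions a residual covariance, a variance by time point or a robust standard error.

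On output, the SAP says: "From the model mean profile by treatment and relevant treatment differences will be estimated and explored". Section 2 of the SAP (Statistical considerations) says that results of a statistical analysis come with the "two-sided 95% confidence interval and corresponding two-sided p-value". The individual points of the profile are a listed supportive secondary endpoint (protocol 4.2.2.1), without the asterisk that marks key endpoints.

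For repeated HbA1c, SAP 2.3.1 does name the covariance: a "linear mixed normal model using an unstructured residual covariance matrix".

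**The concern.** A random subject effect plus independent residuals of constant variance implies the same variance at every time point and the same correlation between any two. The nine points are physiologically unlike: the profile "starts with a pre-breakfast SMBG on day 1 and ends with a pre-breakfast SMBG on the following day", with pre-meal, 90-minute post-meal, bedtime and 4 a.m. readings between (protocol 8.4.1.1). Nothing in the plan suggests that they vary equally.

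The mean model lets the treatment difference vary freely over time, but one pooled variance sets the precision of all nine differences. At stake is the width of nine confidence intervals and the matching p-values. The estimates themselves are not at stake: every fixed effect is a subject-level factor crossed with time, so with complete data the estimated differences are the same under any covariance structure.

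**Working it through.** **Inputs from the documents**
- Nine time points (protocol 8.4.1.1, Table 8–1).
- 105 subjects per arm, 1:1 (protocol 17.1).
- Two-sided 95% intervals (SAP section 2).
- Nearly balanced data, since "Missing values (including intermittent missing values) will be imputed using the LOCF method".

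**The plan's own figure.** There is none for the SMBG model. As a check on n, the HbA1c power does reproduce: 0.85 × 0.45 + 0.15 × 0.20 = 0.4125; with SD 1.0, 105 per arm and a noncentral t on 208 degrees of freedom, power is 84.5%, as stated.

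**Inputs that are assumptions.** No document gives an SMBG standard deviation. I let fasting SD f apply to the two pre-breakfast points and 4 a.m., post-meal SD m to the three 90-minute points, and the midpoint i = (f + m)/2 to pre-lunch, pre-dinner and bedtime.

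**Formulas**
- True SE at point t: SD_t × √(2/105) = SD_t × 0.1380.
- SE from the planned model with the default residual: RMS × 0.1380 at every point, where RMS² is the mean of the nine variances, here (f² + i² + m²)/3.
- Coverage at point t: 2Φ(1.96 × RMS/SD_t) − 1.

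**Worked case, f = 1.5 and m = 2.25.** i = 1.875. RMS² = (2.25 + 3.516 + 5.063)/3 = 3.609, so RMS = 1.900 and the common SE is 0.262. True SEs are 0.207 fasting and 0.311 post-meal. RMS/SD is 1.267 fasting and 0.844 post-meal, so intervals are 27% too wide and 16% too narrow. Coverage is 2Φ(2.48) − 1 = 98.7% and 2Φ(1.655) − 1 = 90.2%.

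**Range**

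| Assumed SD, fasting / post-meal (mmol/L) | Common SE | True SE, fasting / post-meal | Coverage, fasting / midpoint / post-meal |
|---|---|---|---|
| 2.0 / 2.0 | 0.276 | 0.276 / 0.276 | 95.0% / 95.0% / 95.0% |
| 1.5 / 1.8 | 0.228 | 0.207 / 0.248 | 96.9% / 95.1% / 92.8% |
| 1.5 / 2.25 | 0.262 | 0.207 / 0.311 | 98.7% / 95.3% / 90.2% |
| 1.5 / 3.0 | 0.322 | 0.207 / 0.414 | 99.8% / 95.8% / 87.2% |
| 2.25 / 1.5 (reversed) | 0.262 | 0.311 / 0.207 | 90.2% / 95.3% / 98.7% |

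The midpoint assumption matters. If the three intermediate points instead take the fasting SD or the post-meal SD, RMS² becomes (2f² + m²)/3 or (f² + 2m²)/3. Post-meal coverage then runs from 88.0% to 92.3% at 1.5/2.25, and from 83.4% to 91.0% at 1.5/3.0.

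**Check by fitting.** The random-intercept model was fitted by REML to simulated trials with 105 per arm, four pre-trial treatment strata, within-subject correlation 0.5 and SDs 1.5/2.25. In a complete-data fit all nine SEs were 0.2597. Over 254 such trials coverage was 98–99% at fasting points and 89–91% post-meal. With 8% of points missing at random, the nine SEs in one fit ran from 0.262 to 0.268, still practically common.

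**The case against.** The strongest reply is that the text is silent, not wrong. A mixed model can carry a random subject effect together with time-specific residual variances, and neither document rules that out. A reader might infer that the plan forces a common standard error. The documents do not go that far: the covariance is unspecified, and the common SE follows from the ordinary default. That limits the wording of the point, but it does not answer it, because the choice is left to software.

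A reader might also infer, without condition, that intervals will be too wide at fasting points and too narrow after meals. The documents do not show this. They give no SMBG variability; equal SDs produce no error, and reversed SDs flip the direction. What they do offer is plausibility: both arms are titrated on pre-breakfast SMBG (protocol 5.2; Appendix A, 3.3), which should compress fasting variation in particular.

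A third inference would be that the case for a post-meal liraglutide effect rests on this model. It does not. The prandial increments and the profile mean are each analysed by separate ANCOVA, with their own residual variance, and the individual-point differences are only to be explored.

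Finally, the unstructured matrix for HbA1c serves a different purpose, robustness of the primary result to missing visits. The contrast is therefore not a contradiction. It shows only that the sponsor specifies a covariance elsewhere and could do so here.

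**Conclusion.** The point holds as a minor one about specification. As written and read in the ordinary way, the model gives one standard error to nine differences, and interval widths are wrong whenever variances differ across the day. On the assumed SDs, coverage at high-variance points falls from 95% to about 93%, 90% or 87% as the post-meal SD rises from 1.8 through 2.25 to 3.0 against a fasting SD of 1.5. Low-variance points rise to between about 97% and 99.8%. With midpoint SDs, the intermediate points stay within about one percentage point of 95%. These sizes rest on SDs that the documents do not supply and on the default residual; the direction rests on fasting variance being the lower, which is plausible but not shown.

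The scope is one supportive endpoint with no confirmatory claim attached. The primary analysis, the profile mean and the prandial increments are unaffected.

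**What to change.** In SAP 2.4.1.1, replace the random subject effect with an unstructured residual covariance across the nine time points within subject, matching the "unstructured residual covariance matrix" already specified for HbA1c. State the fallback order in advance in case the model does not converge: heterogeneous Toeplitz, then heterogeneous compound symmetry. All three let each point have its own variance, so the fix is sound whether fasting or post-meal variance is larger, or neither.

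The cost is a short SAP edit and a change to the model statement in the program. No new data are needed. The small downside is 9 × 10/2 = 45 covariance parameters, estimated from 210 planned subjects, with possible non-convergence; the fallbacks cover that.
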